4.8.2.1 Association of Immunogenicity with Exposure, Safety and Efficacy

The safety and efficacy analysis mentioned below will be conducted using the following categories:

ADA positive participants: Participants with treatment-emergent or treatment-boosted response.

ADA negative participants: Participants with pre-existing immunoreactivity or negative in the ADA assay at all time points.

Impact of ADA on PK profile

Potential associations between ADA variables (e.g., ADA peak titers, neutralizing antibody status, treatment-emergent, persistent, indeterminate and transient response, treatment-boosted) and impact on serum concentration profile of dupilumab may be explored. Plot of serum concentration of functional dupilumab versus visit will be provided by ADA variables for dupilumab group. Individual participant plots of dupilumab concentration according to ADA status will be provided.

Impact of ADA on clinical efficacy endpoints

Associations between the ADA variables (e.g., ADA peak titers, neutralizing antibody status, treatment-emergent, persistent, treatment-boosted) and the primary efficacy endpoint may be explored for the dupilumab dosed group.

Association of ADA with clinical safety endpoints

Association of safety versus ADA status may be analyzed in the ADA population. The safety assessment may focus on the following events:

- Severe injection site reactions last longer than 24 hours or serious injection site reactions
- Hypersensitivity reactions (SMQ (20000214) hypersensitivity narrow search confirmed by medical review)
- Anaphylactic reactions (SMQ (20000021) anaphylactic reaction narrow search)

Associations between ADA variables (e.g., ADA peak titers, neutralizing antibody status, treatment-emergent, persistent and treatment-boosted) and safety may be explored.

4.8.3 Pharmacodynamic/genomics endpoints

Venous blood samples will be collected at Visit 2 (Week 0), Visit 3 (Week 12), Visit 4 (Week 24/EOT), and Visit 5 (Week 36), for measurement of total serum IgE. Total IgE will be measured using validated quantitative methods.

For those participants (with exception of adolescent) who consent to the optional pharmacogenetic/pharmacogenomic sample collection section of the ICF, serum/plasma for archival samples for possible future analysis of potential biomarkers of drug response, disease activity, safety, and the Type 2 inflammation pathway, and blood samples for exploratory genetic analysis of DNA or RNA will be collected and stored for possible future use. Participation is optional. Participants who do not wish to participate in the genetic research may still participate in the study.

For those participants (with exception of adolescent) who consent to the optional basophil activation (substudy), samples will be taken at Visit 2, Visit 3 (Week 12) and Visit 4 (Week 24/EOT).

Total IgE will be summarized in the safety population defined as participants who actually received at least 1 dose or part of a dose of the IMP. Baseline values will be the last value collected prior to the first IMP. Descriptive statistics (including number, mean, SD, median, Q1, Q3, min, max) of biomarkers at baseline will be summarized.

Summary plots (median+/- standard error of the mean) on values at each visit, absolute changes from baseline and percent changes from baseline will be provided for the total IgE by intervention group and visit.

Exploratory analysis of DNA/RNA will be addressed in a separate document.

The analyses of the basophil activation substudy will be addressed in a separate document.

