1 INTRODUCTION

1.1 STUDY DESIGN

The EFC16720 study is a 24-week, randomized, double-blind, placebo-controlled, parallel-group, multi-center study to evaluate the use of dupilumab in adults and adolescents (≥ 12 to < 18 years old) with primary acquired chronic inducible cold urticaria (ColdU) who remain symptomatic despite the use of H1-antihistamine treatment. The study is designed to test the hypothesis that dupilumab will increase the proportion of participants with a negative ice cube provocation test at Week 24 compared with placebo. A negative ice cube provocation test is defined as the absence of a confluent hive/wheal at the entire skin site of exposure after an ice cube provocation test.

The study consists of 3 periods:

- Screening period (2 to 4 weeks).
- Randomized IMP treatment period (24 weeks).
- Post IMP treatment period (12 weeks).

Chronic inducible ColdU signs and symptoms will be evaluated after the ice cube provocation test, by the Investigator (hives/wheals intensity) and participant (itch severity, skin pain, skin sensation). In addition, chronic inducible ColdU disease activity will be assessed daily by the participant using ColdUAS questionnaire in an e-diary where the participant will report his/her skin reactions (wheals and swelling), skin sensations (itching, burning, pain or feeling hot), if they have been in contact with cold temperatures that usually cause skin reactions, if they have avoided trigger exposure, and overall symptoms severity. The study will also assess the effect of dupilumab on urticaria control, participants' HRQoL and overall health status, proportion of patients with cold urticaria requiring emergency medical care visit or treatment with epinephrine and on reduction of rescue therapy.

The total anticipated number of participants randomized in the study is 78. This corresponds to approximately 39 participants who will be randomly assigned to each intervention arm:

- Dupilumab: 300 mg every q2w for adults; 200 mg q2w for adolescents ≥ 30 kg and < 60 kg at baseline or 300 mg q2w for adolescents ≥ 60 kg at baseline.
- Matched placebo.

At least 4 participants randomized in the study will be adolescents (≥ 12 to < 18 years old) who will be recruited in a few selected sites in selected countries. Randomization will be stratified by age (adolescent versus adult) and within adult group by country and background H1-antihistamine regular/daily use (Yes/No).

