
Objectives	Endpoints

• To evaluate immunogenicity of dupilumab	
• Incidence of treatment-emergent antidrug antibodies (ADA) against dupilumab over time
Tertiary/exploratory	

Pharmacokinetic (PK)/Pharmacodynamic (PD)

- To evaluate PK of dupilumab
- To evaluate PD effect of dupilumab
- Functional dupilumab concentrations in serum and PK profile
- Total immunoglobulin E over time.

a Provocation test reading time for all endpoints: 15 minutes after the ice cube application start = 5 minutes ice cube application plus 10 minutes after removal of ice cube

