2 SAMPLE SIZE DETERMINATION

Sample size is calculated based on the following assumptions:

1. The placebo group has █ participants with negative ice cube provocation test at Week 24 and the dupilumab group has █ participants with negative ice cube provocation test at Week 24.
2. There is a drop-out rate of 10% in both groups.
3. The statistical test is a Z test that is based on the difference of the 2 proportions with unpooled variance estimate and 2-sided 1% significance level.
4. Participants are equally randomized to the dupilumab group and the placebo group.

With these assumptions, 39 participants per group (78 participants in total) will provide 90% power to detect the difference of █ response rate in the dupilumab group and █ response rate in the placebo group. The sample size calculations were performed using nQuery+nTerim 4.0.

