4.3.5 Subgroup analyses

To assess the homogeneity of the treatment effect across various subgroups, analyses will be performed on the primary endpoint across the following subgroups:

- Age group (< median, \geq median; adult, adolescent)
- Gender (Male, Female)
- Baseline weight (< median, \geq median, <60 , ≥ 60 kg)
- Baseline BMI (<25 , ≥ 25 - <30 , ≥ 30 kg/m²)
- Region (see [Section 5.3](#))
- Race (White, all the Others)
- Ethnicity (Hispanic, non-Hispanic)
- Baseline H1-AH use (regular vs per-need)
- Baseline serum Total IgE (<100 IU/mL, ≥ 100 IU/mL)
- Duration of cold urticaria before screening visit (<5 , ≥ 5 years)
- History of allergy (Allergic, non-Allergic)
- History of angioedema

To assess the consistency of the treatment effects across the subgroup levels, subgroup analyses will be conducted for the primary endpoint at Week 24. The analysis will be performed based on imputed datasets from the primary analysis.

To test the interaction between intervention and subgroup factor, a logistic regression model incorporating subgroup-by-treatment interaction will be built for each subgroup factor. The model will include all the covariates in the main statistical model plus the subgroup variable (if not one of the covariates adjusted in the main model already) and the subgroup-by-treatment interaction.

In each subgroup, the primary endpoint will be analyzed using the primary approach for the primary endpoint, but on the specific subgroup. Forest plots will be provided.

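### The total IgE plots put the standard error of the mean around a median, so the bar shows neither the median's uncertainty nor the spread of the data (minor correction).

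*SAP*

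**What the plan says.** SAP 4.8.3 specifies "Summary plots (median+/- standard error of the mean) on values at each visit, absolute changes from baseline and percent changes from baseline" and adds that these "will be provided for the total IgE by intervention group and visit". There are therefore three panels: values, absolute changes and percent changes. They serve the exploratory pharmacodynamic endpoint "Total immunoglobulin E over time" (SAP 1.2, Table 1).

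The same section says "Total IgE will be summarized in the safety population". It names quartiles once, for baseline only: "Descriptive statistics (including number, mean, SD, median, Q1, Q3, min, max) of biomarkers at baseline will be summarized".

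Two other places bear on IgE after baseline. SAP 5.4 (Appendix 4) plans by-visit descriptive summaries of the pharmacokinetic and pharmacodynamic variables, and total IgE has its own windows in Table 11 for Weeks 0, 12, 24 and 36. SAP 4.1 sets the default statistics for continuous data: number, mean, SD, median, minimum and maximum. Neither place changes the error bar in 4.8.3.

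**The concern.** A reader takes an error bar as a statement about the point it is drawn on. Here the point is a median, while the bar is SD/√n, which belongs to the mean. In right-skewed data the SD is driven by the few highest values, so one or two participants with very high IgE could widen the bar while the median hardly moves. A symmetric bar is also the wrong shape for skewed values and can extend below zero, which an IgE concentration cannot do.

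At stake is how the pharmacodynamic figure in the study report is read. Bars that are too wide can mask a separation of the medians or suggest instability. Bars that are too narrow overstate precision.

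Elsewhere the SAP pairs its statistics properly. Laboratory and vital-sign plots use mean change with its own standard error (4.7.3.1), and peak antibody titers are summarized by median with quartiles and range (4.8.2).

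**Working it through.** The plan states no figure that depends on this point, so there is nothing to reproduce. The check compares the bar as specified with the standard error (SE) of the median.

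**Inputs from the documents**
- Bar: median ± SEM (SAP 4.8.3).
- Arm size: "This corresponds to approximately 39 participants who will be randomly assigned to each intervention arm" (SAP 1.1).
- Dropout: "There is a drop-out rate of 10% in both groups" (SAP 2), so later visits have about 39 × 0.90 ≈ 35 per arm.
- IgE distribution: none given. The only level stated is the subgroup cut "Baseline serum Total IgE (<100 IU/mL" (SAP 4.3.5).

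**Assumption.** IgE values are log-normal with median m and log-SD s. Since s is unknown, a range is shown.

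**Formulas**
- Population SEM = m · exp(s²/2) · √(exp(s²) − 1) / √n
- Large-sample SE of the median = √(π/2) · s · m / √n = 1.2533 · s · m / √n

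**Worked at n = 39 (√39 = 6.245)**
- s = 0.5: SEM = 1.133 × 0.533 / 6.245 = 0.097m; SE of median = 0.627 / 6.245 = 0.100m; ratio 0.96.
- s = 1.0: SEM = 1.649 × 1.311 / 6.245 = 0.346m; SE of median = 1.253 / 6.245 = 0.201m; ratio 1.72.
- s = 1.5: SEM = 3.080 × 2.913 / 6.245 = 1.437m; SE of median = 1.880 / 6.245 = 0.301m; ratio 4.77.
- Normal data, for comparison: ratio = 1/√(π/2) = 0.80, so the bar is too narrow.

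The plot will show the sample SEM. In skewed data of this size it usually falls below the population value, because the extreme tail is often not sampled. Drawing 200,000 simulated arms of 39 gives the following (ratios from unrounded values):

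| s | Typical (median) sample SEM | SE of median | Typical ratio | Average ratio | Lower bar below zero |
|---|---|---|---|---|---|
| 0.5 | 0.092m | 0.101m | 0.92 | 0.94 | 0.0% |
| 1.0 | 0.279m | 0.205m | 1.36 | 1.52 | 0.6% |
| 1.5 | 0.761m | 0.320m | 2.37 | 3.18 | 33% |

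With 35 per arm the typical ratios are 0.91, 1.33 and 2.29, and the lower bar is below zero in 0.0%, 0.9% and 35% of arms. Dropout hardly matters.

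**Change panels.** A negative bar is impossible only for raw values, since absolute and percent changes can properly be negative. For percent change, assuming a median fall of 55% and a log-SD of 0.2, 0.4 or 0.8 for the ratio to baseline, the typical SEM is 0.81, 0.87 or 1.13 times the SE of the median. The width error there may be small, although the bar is still the wrong statistic. Absolute change was not simulated.

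**The case against.** The strongest case on the other side is that this is a presentation detail on an exploratory endpoint. Total IgE is not in the testing hierarchy (SAP 4.6) and no IgE test is planned. The plotted medians are themselves correct. The wording may be a slip for mean ± SEM, or for a median with quartiles. All of this stands, and it limits the weight of the point. It does not remove it: a programmer following 4.8.3 literally would produce the mismatched figure, and the documents do not show which alternative was meant.

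Three stronger readings are tempting, and the documents do not support them.
- A reader of 4.8.3 alone might infer that these plots are the only post-baseline display of IgE. SAP 5.4 with Table 11 plans by-visit descriptive summaries, and SAP 4.1 supplies their default statistics, including the SD and range.
- A reader might infer that the bars are necessarily several times too wide. The population-SEM ratios of 1.7 and 4.8 overstate what one plotted arm would typically show (about 1.4 and 2.4). With low skew the bar is slightly too narrow. As the documents give no IgE spread, even the direction is not established from them.
- A reader might carry the below-zero problem over to all three panels. It applies only to raw values.

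**Conclusion.** The error bar is wrong as written. That conclusion needs no distributional assumption, because the SEM is not the precision of a median under any distribution and nothing elsewhere in the SAP corrects the text.

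Its size in the values panel rests on assumed log-normality and 39 per arm. The typical bar runs from slightly too narrow at log-SD 0.5 to about 1.4 times the SE of the median at 1.0 and about 2.4 times at 1.5. A lower bar below zero is rare at log-SD 1.0 and occurs in about a third of arms at 1.5. For percent change the width error may be negligible.

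This is a minor correction to a descriptive figure. It has no bearing on alpha, power, sample size, the estimands or the testing hierarchy.

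**What to change.** In SAP 4.8.3, replace the SEM bar with one that belongs to the median, for values, absolute changes and percent changes alike. Use Q1 and Q3 if the figure is meant to show spread, or a distribution-free 95% confidence interval for the median if it is meant to show uncertainty. State in the legend which is drawn. For positive IgE values, neither can fall below zero in the values panel, because quartiles and order-statistic limits lie within the observed range.

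A geometric mean with a back-transformed log-scale interval is an alternative for the values panel or for the ratio to baseline only. It cannot be applied to absolute or percent changes, which may be zero or negative and so have no logarithm.

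The cost is one line of the SAP and one option in the plot program, with no new data.

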4.9 INTERIM ANALYSES

No interim analysis is planned.

A primary database lock will be performed when all randomized participants in this study have completed their 24-week treatment phase. Analysis will be based on all data collected up to the database cut-off date and will be considered as the final analyses in the CSR.

The database will be updated at the end of the study for all participants to include the post-treatment follow-up information and updates for the events previously ongoing at the time of the primary lock. Additional data between this database lock and last participant completing last visit will be summarized in a CSR addendum.

5 SUPPORTING DOCUMENTATION

5.1 APPENDIX 1 LIST OF ABBREVIATIONS

ADA:	anti-drug antibody
AE:	adverse event
AESIs:	adverse events of special interest
ALT:	alanine aminotransferase
ANCOVA:	analysis of covariance
AST:	aspartate aminotransferase
ATC:	anatomic category
CDG:	customized drug grouping
CDLQI:	Children's Dermatology Life Qualtiy Index
CI:	confidence interval
CLcr:	Creatinine clearance
CSU:	Chronic Spontaneous Urticaria
DLQI:	Dermatology Life Quality Index
DNA:	deoxyribonucleic acid
ECG:	electrocardiogram
eCRF:	electronic case report form
EOT:	end of treatment
HBc Ab:	hepatitis B core antibody
HBs Ab:	hepatitis B surface antibody
HBs Ag:	hepatitis B surface antigen
HBV:	hepatitis B virus
HCV Ab:	hepatitis C virus antibodies
HLGT:	high level group term
HLT:	high level term
HRQoL:	health-related quality of life
IMP:	investigational medicinal product
ITT:	intent-to-treat
LLT:	lower-level term
LS:	least squares
MedDRA:	medical dictionary for regulatory activities
OCS:	oral corticosteroids
PCSA:	potentially clinically significant abnormality
PGIS:	Patient Global Impression of Severity
PT:	preferred term
RNA:	ribonucleic acid
SAP:	statistical analysis plan
SDG:	standardized drug grouping
SDGs:	Standardized drug groupings
SMQ:	standardized MedDRA query
SOC:	system organ class

TEAE:	treatment-emergent adverse event
UCT:	urticaria control test
ULN:	upper limit of normal
WHO-DD:	World Health Organization-Drug Dictionary

5.2 APPENDIX 2 CHANGES TO PROTOCOL-PLANNED ANALYSES

This Statistical Analysis Plan (SAP) for study EFC16720 is based on the protocol amendment 01 dated 27 September 2022. For the details of major statistical changes, see protocol amendment summary of changes table in study protocol.

5.3 APPENDIX 3 DEMOGRAPHICS AND BASELINE CHARACTERISTICS, PRIOR OR CONCOMITANT MEDICATIONS

Demographics, baseline characteristics, medical surgical history

The following demographics and baseline characteristics, medical and surgical history and disease characteristics at baseline will be summarized using descriptive statistics in the randomized population.

Demographic variables are

- Age in years (quantitative and qualitative variable: 12-<18, 18-<40, 40-<65, 65-<75 and ≥ 75 years),
- Gender (Male, Female),
- Race (White, Black or African American, Asian, American Indian or Alaska Native, Native Hawaiian or other Pacific Island, unknown),
- Ethnicity (Hispanic or Latino, Not Hispanic or Latino, Unknown)
- Region (**Asia**: Japan; **Latin America**: Argentina; **Western Countries**: Canada, USA, Germany)
- Weight in kg (quantitative and qualitative variable: <60, ≥ 60 kg)
- BMI in kg/m² (quantitative and qualitative variable: <30, ≥ 30 kg/m²)

Baseline safety and efficacy parameters (apart from those listed above) will be presented along with the safety and efficacy summaries.

Medical (or surgical) history includes all the relevant medical (or surgical) history during the lifetime of the participant.

This information will be coded using the version of MedDRA currently in effect at Sanofi at the time of database lock.

Comorbidity will be summarized separately. The following comorbid diseases will be summarized from electronic case report form (eCRF) pages which were filled in by investigators based on participant reporting. Angioedema history will be further summarized under disease characteristics at baseline.

CSU (Yes, Ongoing condition)

Atopic Dermatitis (Yes, Ongoing condition)

Allergic rhinitis (Yes, Ongoing condition)

Allergic Conjunctivitis (Yes, Ongoing condition)

Asthma (Yes, Ongoing condition)

Food allergy (Yes, Ongoing condition)

Chronic Rhinosinusitis (Yes, Ongoing condition)

Nasal Polyps (Yes, Ongoing condition)

Eosinophilic Esophagitis (Yes, Ongoing condition)

Disease characteristics at baseline

The following baseline disease characteristics will be summarized by intervention group:

- Age at onset of cold urticaria (years)
- Duration of cold urticaria before screening visit (years) to be derived as
- (Year of screening visit – Year of first diagnosis of cold urticaria) + (month of screening visit-month of first diagnosis of cold urticaria)/12
- Number of patients who had cold urticaria events within 12 months before screening visit requiring Hospitalization/emergency care [n (%)], Epinephrine [n (%)] and OCS [n (%)], resulting in anaphylactic reaction [n (%)] and oropharyngeal edema [n (%)]
- Number of patients who experienced cold urticaria symptoms including Skin (e.g. Localized Urticaria) [n (%)], Angioedema (e.g. Oropharyngeal angioedema) [n (%)], Skin (e.g. Generalized Urticaria) [n (%)], Skin (e.g. Generalized Urticaria) [n (%)], Generalized Angioedema [n (%)], Respiratory distress (e.g. Wheezing or shortness of breath) [n (%)], Hypotension (e.g. Dizziness, sensation of fainting, disorientation, or shock) [n (%)], Gastrointestinal discomfort (e.g. Diarrhea or vomiting) [n (%)], Other symptoms [n (%)]
- Baseline urticaria control test (UCT)
- Baseline Wheal intensity Likert scale
- Baseline peak pruritus NRS
- Baseline peak pain NRS

- Baseline peak burning sensation NRS
- Baseline number of cold urticaria sign and symptom free days, Baseline number of cold exposure days, Baseline number of days of avoidance to cold (all measured by ColdUAS)
- Baseline proportion of cold urticaria sign and symptom free days (measured by ColdUAS)
- Baseline cold urticaria signs and symptoms severity on cold exposure (measured by ColdUAS)
- Baseline Dermatology Life Quality Index (DLQI)/Children's Dermatology Life Quality Index (CDLQI)
- Baseline ColdU-QoL
- Baseline Patient Global Impression of Severity (PGIS)
- Screening ACUSI
- Baseline EQ-5D-5L and EQ-VAS
- Baseline IgE (quantitative and qualitative variable : <100 vs \geq 100)
- Baseline H1-AH use (regular vs per-need) and dose (<1-fold, 1-fold, 2-3-fold, 4-fold)
- Prior cold urticaria medication use (LTRAs, H2-blockers, Omalizumab)

Prior or concomitant medications

All medications taken within 1 month before screening and until the end of the study, including all prior medications taken for ColdU are to be reported in the case report form pages.

All medications will be coded using the World Health Organization-Drug Dictionary (WHO-DD) using the version currently in effect at Sanofi at the time of database lock.

- Prior medications are those the participant used prior to first investigational medicinal product (IMP) injection. Prior medications can be discontinued before first administration or can be ongoing during treatment phase.
- Concomitant medications are any interventions received by the participant concomitantly to the IMP, from first administration of IMP to last IMP intake + 98 days.
- Post-treatment medications are those the participant took in the period running from the end of the concomitant medications period up to the end of the study.
- A given medication can be classified as a prior medication and/or as a concomitant medication and/or as post-treatment medication. If it cannot be determined whether a given medication was taken prior or concomitantly or post, it will be considered as prior, concomitant, and post-treatment medication.

The prior and concomitant medications will be summarized for the randomized population

Medications will be summarized by intervention group according to the WHO-DD dictionary, considering the first digit of the anatomic category (ATC) class (anatomic category) and the

first 3 digits of the ATC class (therapeutic category). All ATC codes corresponding to a medication will be summarized, and participants will be counted once in each ATC category (anatomic or therapeutic) linked to the medication. Therefore, participants may be counted several times for the same medication.

Prior medications will be summarized separating for those taken for ColdU versus other reasons. The tables for prior medications will be sorted by decreasing frequency of ATC followed by all other therapeutic classes based on the overall incidence across intervention groups. In case of equal frequency regarding ATCs (anatomic or therapeutic categories), alphabetical order will be used.

Concomitant medication received during first IMP to last IMP +14 days and concomitant medication received during first IMP to last IMP +98 days will be summarized separately. The tables for concomitant medications will be sorted by decreasing frequency of ATC followed by all other therapeutic classes based on the incidence in the dupilumab group. In case of equal frequency regarding ATCs (anatomic or therapeutic categories), alphabetical order will be used.

Medications will also be summarized by generic name sorted by decreasing frequency based on the incidence in the dupilumab group.

Rescue medications

The following rescue medications may be used:

- Additional doses of H1-AH up to 4-fold the recommended dose (2-fold in Japan)
- Short course of OCS

The use of rescue medications should be delayed, if possible, for at least 8 weeks following the initiation of IMP. The following specific medications will be summarized:

- Rescue medications taken during the study will be summarized separately overall and by type (additional doses of H1-AH medications, OCS therapy).
- The total number of days rescue medication was taken by type will be summarized.

